10.6.2 Analysis of Secondary Immunogenicity Endpoint(s)

- Seroconversion rate (SCR) of antigen-specific antibody (Anti-S1-RBD) on Day 57

The SCR will be presented as count and percentage in frequency table, and the 95% exact (Clopper-Pearson) confidence interval will be provided as well by study group. Fisher's exact test will be used for the comparison of UB-612 vaccine group and placebo group. Summary of descriptive statistics by age group will be also performed.

- Geometric mean titer (GMT) of SARS-CoV-2 neutralizing antibody on Day 197 and 365

GMT and 2-sided 95% CIs will be provided for each study group. Additionally, the difference between UB-612 vaccine and placebo groups will be analysed by ANCOVA model under log-transform data with baseline level as covariate and effect of study treatment, if appropriate. Summary of descriptive statistics by age group will be also performed.

In addition, the GMT of SARS-CoV-2 neutralizing antibody on Day 365 for subjects received two vaccinations and three vaccinations should be analysed separately. Analysis of GMT of SARS-CoV-2 neutralizing antibody on Day 365 for subjects received third dose of UB-612 will be performed with the Evaluable Booster Population only.

- Geometric mean titer (GMT) of antigen-specific antibody (Anti-S1-RBD) on Day 57, 197, and 365

GMT and 2-sided 95% CIs will be provided for each study group. Additionally, the difference between UB-612 vaccine and placebo groups will be analysed by ANCOVA model under log-transform data with baseline level as covariate and effect of study treatment, if appropriate. Summary of descriptive statistics by age group will be also performed.

In addition, the GMT of Anti-S1-RBD on Day 365 for subjects received two vaccinations and three vaccinations should be analysed separately. Analysis of GMT of Anti-S1-RBD on Day 365 for subjects received three vaccinations will be performed with the Evaluable Booster Population only.

- Geometric mean fold increase in antigen-specific antibody (Anti-S1-RBD) and SARS-CoV-2 neutralizing antibody on Day 57, 197 and 365

GMFI and 2-sided 95% CIs will be provided for each study group. Additionally, the difference between UB-612 vaccine and placebo groups will be analysed by Student's t test under log-transform data. Summary of descriptive statistics by age group will be also performed.

In addition, the GMFI of Anti-S1-RBD on Day 365 for subjects received two vaccinations and three vaccinations should be analysed separately. Analysis of GMFI of Anti-S1-RBD on Day 365 for subjects received third dose of UB-612 will be performed with the Evaluable Booster Population only.

- Lot consistency as assessed by the comparisons of the GMT of SARS-CoV-2 neutralizing antibody on Day 57 induced by 3 independent UB-612 vaccine clinical materials. The 95% confidence intervals between groups will be within the margin of 0.5 to 2.

For lot consistency, the 1 month after 2nd vaccination, for all pairs of lots, the two sided 95% CIs for the GMT ratios (GMTR) of neutralizing antibody will be calculated. For all pairs of lots, if the two-sided 95% CIs for the GMTR are within the [0.5,2.0] clinical limit interval, lot consistency will be concluded. The GMTR will be calculated as the mean of the difference of decimal logarithmically transformed antibody titers and exponentiating the mean with base 10. The associated 2-sided CIs will be obtained by calculating CIs using Student's t-distribution for the mean difference of the logarithmically transformed antibody titers and exponentiating the confidence limits with base 10.

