All subjects will come back on Day 197, Visit 5, for immunogenicity persistence check in immunogenicity group and safety check for safety group. **Once subject completes Visit 5, he or she will be unblinded. Subjects received placebo will withdraw from the study and subjects who received UB-612 vaccine will be invited to join the extension study to determine the durability of the immune response and long-term safety after unblinding. Meanwhile, subjects in vaccine group will be encouraged to have a third dose of UB-612. All subjects who received UB-612 vaccine will be followed up for 12 months.**

All subjects will receive safety calls on Day 8, Day 15, Day 22, Day 36, Day 43, Day 64, Day 71, Day 78, Day 85, Day 253, and Day 309 that will serve both to monitor for unsolicited AEs or/and to monitor for symptoms of COVID-19. After Day 57, each week (i.e., every 7 days) the subject will receive a prompt on their smartphone device to regularly surveillance for signs and symptoms of COVID-19 and SAE. **Subjects who received 3rd dose of UB-612 will receive an extra safety call on 7 days post 3rd vaccination.**

If a Grade 3 local reaction, systemic event, or fever are reported in the reactogenicity e-diary, a telephone contact should occur to ascertain further details and determine whether a site visit is clinically indicated. If suspected Grade 4 local reaction systemic event and /or fever is reported in the reactogenicity e-diary, a site visit should occur to confirm whether the event meets the criteria for Grade 4. All subjects were encouraged to contact site staff once they encountered Grade 3/4 AE. Allergic skin reaction should be monitored for 14 days post vaccination and should be contacted regardless of severity.

If a subject experiences a febrile illness associated with respiratory symptoms, he or she is instructed to contact the site immediately. Subjects may utilize a COVID-19 illness e-diary to prompt him/her to report any symptoms.

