7.3 Discussion of Study Design

The primary objectives of this study are to evaluate the immune response after full immunization. Secondary objectives are to evaluate persistence of immune response, and safety and tolerability of UB-612 vaccine to prevent SARS-CoV-2 infection up to 12 months. COVID-19 can affect anyone, and the disease can cause symptoms ranging from mild to very severe. For some other illnesses caused by respiratory viruses (such as influenza), some people may be more likely to have severe illness than others because they have characteristics or medical conditions that increase their risk. These are commonly called “risk factors.” Examples include older age or having certain underlying medical conditions. Older adults are at greatest risk of severe disease and death due to coronavirus disease 2019 (COVID-19). Globally, persons older than 65 years comprise 9% of the population, yet account for 30% to 40% of cases and more than 80% of deaths [13]. COVID-19 is a new disease. Currently there are limited data and information about the impact of many underlying medical conditions on the risk for severe illness from COVID-19. In this study design, adults of any age might be at an increased risk for severe illness from the virus that causes COVID-19 as defined who had at least one of the Charlson comorbidity index [14] category or obesity only (BMI ≥ 30 kg/m²).

Per EUA requirement issued by TFDA, the sponsor should submit the lot-to-lot consistency report to demonstrate the quality of vaccine product. Core group is designed for EUA application. Among 3850 subjects, 462 evaluable subjects aged from >18 to < 65 will be enrolled for lot-to-lot consistency. Additional 350 evaluable adult subjects will be assigned into immunogenicity study. In order to demonstrate vaccine efficacy in elderly, authority requests EUA package should include at least 600 elder subjects who received the vaccine. Thus we plan to enrol around 770 randomized subjects aged from ≥ 65 to 85 years old, in which at least 154 evaluable subjects will have immunogenicity data to compare with young adults. After completion recruitment of the core group, 385 adolescents will be randomly recruited as supplementary group to extend vaccine indication. At least 154 evaluable adolescents (allocation rate 6:1) will have immune data to compare with adults.

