7.4.4.2 Criteria for Discontinuation of Study Treatment

The following conditions constitute a contraindication to vaccination and should be checked prior to second **and third vaccinations**:

1. Has any Grade 4 adverse reaction related to IP within 7 days after **previous vaccination**.
2. Has any SAE related to **previous** dose related to IP during the follow-up of **previous vaccination**.
3. Subject has or develops the symptom or condition listing in 1 or more exclusion criteria.
4. Subject diagnoses with SARS-CoV-2 infection or has suspected SARS-CoV-2 infection based on symptoms according to investigator's judgment (lab test conformation is not necessary).
5. Subject becomes pregnant.
6. Any condition that in the opinion of the investigator would be a contraindication to **vaccinations**.

Any subjects who receive the vaccination with dosage deviation or who does not receive the second **and third** vaccination on schedule may not necessarily be withdrawn from the study as further study procedures and the follow-up visits may be performed which will be decided by sponsor.

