10.3 Analysis Populations

Enrolled Population

Enrolled Population includes subjects who have a signed ICF.

Randomized Population

Subjects who are assigned a random number be regarded as Randomized Population.

Evaluable Immunogenicity Population

Evaluable Immunogenicity Population will consist of all eligible randomized subjects who are assigned to lot-to-lot and immunogenicity group, receive two vaccinations within the predefined window, have a valid immunogenicity result at visit 4 (Day 57), have no major protocol deviations or protocol deviations having impact on immunogenicity data. Evaluable Immunogenicity Population will be regarded as primary population for immunogenicity evaluation on primary and secondary immunogenicity endpoints except lot-to-lot consistency.

Evaluable Lot-to-Lot Population

Evaluable Lot-to-Lot Population is a subset of Evaluable Immunogenicity but only includes subjects who are assigned to lot-to-lot consistency group and have immunogenicity determination at Day 57. Evaluable Lot-to-Lot Population will be used for evaluating lot-to-lot consistency only.

Evaluable Efficacy Population

All eligible randomized subjects who receive two vaccinations within the predefined window and have no major protocol deviations or protocol deviations having impact on immunogenicity data will be the Evaluable Efficacy Population. Evaluable Efficacy Population will be used to evaluate vaccine efficacy in exploratory analysis.

Available Immunogenicity Population

Available Immunogenicity Population will consist of all eligible randomized subjects who receive at least one vaccination, and have at least one post immunogenicity data determination. Available Immunogenicity Population will also be used to the immunogenicity evaluation except lot-to-lot consistency.

Evaluable Booster Population

All eligible randomized subjects who receive third dose of UB-612 within the predefined window and have no major protocol deviations or protocol deviations having impact on immunogenicity data will be the Evaluable Booster Population. Evaluable Booster

Population will be used to explore the immunogenicity evaluation after the booster vaccination.**Safety Population**

Safety Population (SAF) will consist of all subjects who received at least one vaccination. The Safety Population is for safety evaluation in analysis.

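### V-205's two-dose Day 365 titres come only from vaccinees who did not take dose 3, so the Day 57, 197 and 365 GMTs do not describe persistence in one cohort

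*Supplement*

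**What the plan says.** All references are to the V-205 protocol.

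- **Population.** Section 10.3: "Evaluable Immunogenicity Population will be regarded as primary population for immunogenicity evaluation on primary and secondary immunogenicity endpoints except lot-to-lot consistency". Its members must "receive two vaccinations within the predefined window, have a valid immunogenicity result at visit 4 (Day 57"); what happens with dose 3 later plays no part in membership.
- **Day 57 and Day 197.** Sections 10.6.1 and 10.6.2 summarise GMTs by study group. The wording in 10.6.2 is "GMT and 2-sided 95% CIs will be provided for each study group", with descriptive summaries by age group.
- **Day 365.** Section 10.6.2 adds that "the GMT of SARS-CoV-2 neutralizing antibody on Day 365 for subjects received two vaccinations and three vaccinations should be analysed separately". It says the same for the anti-S1-RBD GMT and the anti-S1-RBD fold increase, and assigns the three-dose analyses to the Evaluable Booster Population.
- **Who gets dose 3.** After unblinding at Visit 5, section 7.1 says: "Meanwhile, subjects in vaccine group will be encouraged to have a third dose of UB-612". Section 8.1.9 limits the dose to subjects who agree, after a contraindication check. The list in section 7.4.4.2 opens "The following conditions constitute a contraindication to vaccination and should be checked prior to second" and goes on to name the third vaccination too.
- **Purpose.** Section 7.3: "Secondary objectives are to evaluate persistence of immune response". Section 6.4 lists GMTs at Day 197 and Day 365 as secondary endpoints.
- **Synopsis.** The statistical analysis paragraph says that two-dose and three-dose subjects will be summarised separately, and names no time point.

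**The concern.** Persistence is a question about change over time in the same people. As section 10.6.2 is written, the first two points describe every evaluable vaccinee with a sample, and the third describes whoever remains after a voluntary, health-screened offer of another dose. If non-takers already had higher or lower titres than takers at Day 57 or Day 197, the step to Day 365 mixes true waning with a change in who is counted, and the reported figures would not let a reader separate the two.

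What is at stake is the interpretation of a secondary endpoint, durability after two doses. No decision rule hangs on it.

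**Working it through.** **1. Base count.** Section 7.4.6 gives 812 evaluable young adults and 154 evaluable elderly, allocated 6:1. Vaccinees: 812 × 6/7 = 696 and 154 × 6/7 = 132, total 828. This reproduces the protocol's figures exactly.

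**2. Who contributes at each visit.**

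- Day 57: vaccinees in the Evaluable Immunogenicity Population, up to 828 as planned.
- Day 197: the same people, less drop-out; missing values are not imputed (section 10.10). No split by later dose-3 status.
- Day 365, two-dose: only the part of that set without dose 3, meaning those who declined, were contraindicated or did not attend within Day 197 to 242.

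No section asks for the earlier values in this last group, for a paired or weighted analysis, or for a comparison of takers with non-takers. The plan does use a within-subject comparison for the booster question (section 10.7, paired t test against the pre-dose value). It has no counterpart for persistence.

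**3. Fold increase does not mend this.** Each subject is divided by his or her own Day 1 baseline, but that does not keep the same subjects across visits. In V-122 every group had a Day 0 GMT of 10.00 (anti-S1-RBD) and 2.50 (neutralizing), according to Table 5-1 of V-123. If V-205 baselines are similar, fold increase is close to GMT divided by a constant and carries the same change of cohort.

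**4. Possible size.** Let u be the share taking dose 3, and d the mean log10 Day 57 titre of non-takers minus that of takers.

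- Mean of all vaccinees = u × takers + (1 − u) × non-takers.
- Non-takers minus all vaccinees = u × d.
- The unmatched Day 365/Day 57 ratio is therefore off by the factor 10^(u × d).
- Two-dose n at Day 365 = 828 × (1 − u), before other losses.

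The documents give neither u nor d. Assumed: u from 50% to 95% and d = ±0.2 log10, which is one third of the planning SD of 0.6 in section 10.2.2.

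| u (assumed) | Two-dose n | Factor, d = −0.2 | Factor, d = +0.2 |
|---|---|---|---|
| 50% | 414 | 0.79 | 1.26 |
| 70% | 248 | 0.72 | 1.38 |
| 80% | 166 | 0.69 | 1.45 |
| 90% | 83 | 0.66 | 1.51 |
| 95% | 41 | 0.65 | 1.55 |

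With matched subjects the factor is 1 by construction.

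**5. Precision.** The 95% CI of a single-visit GMT extends by about 10^(1.96 × 0.6/√n) each way: a factor of 1.10 at n = 828, 1.14 at 414, 1.23 at 166, 1.35 at 83 and 1.53 at 41.

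**The case against.** The best case against the point has five parts.

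- **This is SAP detail.** Section 10.1 defers full detail to an SAP that is not shown, and a matched table may be in it. That is possible. But section 10.6.2 already fixes the split, the visit and the population, and following it as written produces the mismatch.
- **No decline curve is planned.** Correct. A reader might infer that V-205 specifies a waning curve or a Day 365/Day 197 ratio; it specifies neither. The difficulty arises when the listed GMTs are read in sequence, which a persistence endpoint invites.
- **The synopsis may already split every visit.** Its sentence can be read that way, which would supply part of what is missing. Section 10.6.2 names only Day 365, so the two need aligning.
- **Age mix is handled.** This stands. Section 10.6.2 requires summaries by age group, so a different share of elderly subjects among non-takers is not a good reason for the change. Health, infection history and willingness are not covered.
- **Matching does not cure everything.** This stands too. The matched estimate still describes non-takers only. Diagnosed or suspected infection is a contraindication to dose 3 (section 7.4.4.2), while infected subjects remain in the study (section 7.4.8.5). Infection-raised titres could therefore gather in the two-dose group, and pairing would not take them out.

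The split itself is sound. Pooling boosted and unboosted subjects at Day 365 would be worse.

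**Conclusion.** The point holds as a mismatch of cohorts: the Day 57 and Day 197 GMTs cover all evaluable vaccinees in the immunogenicity and lot-to-lot groups, while the two-dose Day 365 values cover only a self-selected part of them. Read together, they do not measure two-dose persistence.

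Stronger readings are not supported. A reader might infer that the two-dose group must be small, but uptake is not stated, and at 50% it would be 414 of 828. A reader might also infer that waning is overstated, or understated, in a known direction. Refusal, contraindication and infection could push titres either way, and the protocol gives no infection rate and no titre difference. The range 0.65 to 1.55 rests wholly on the assumed 0.2 log10 difference and 50% to 95% uptake; it is not an estimate of the bias.

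**What to change.** In section 10.6.2, or in the SAP before Day 365 data are analysed:

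1. Keep the two-dose/three-dose split at Day 365.
2. For two-dose subjects with a Day 365 sample, report their own Day 57, Day 197 and Day 365 GMTs, and the paired GMT ratios 197/57 and 365/197 with 95% CIs, overall and by age group.
3. Beside these, show the Day 57 and Day 197 GMTs of dose-3 recipients from the immunogenicity and lot-to-lot groups, so that the selection can be seen. Dose-3 recipients from the safety check group have no scheduled immune-response sample at those visits.
4. Label the two-dose Day 365 result as describing a self-selected group.
5. Make the synopsis sentence name the same time points as section 10.6.2.

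**Cost.** One table, with no new visit, sample or subject. The matched estimates use fewer people and have wider intervals than the all-vaccinee values. Self-selection and intercurrent infection remain as limits to be stated.

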10.7 Analysis of Exploratory Endpoint(s)

- T cell responses to UB-612 measured by ELISpot and flow cytometric assays on Day 57

T cell responses to UB-612 measured by ELISpot and flow cytometric assays on Day 57 will be summarized by descriptive statistics.

- **T cell responses to UB-612 measured by ELISpot and flow cytometric assays on 14 days post 3rd dose of UB-612**

T cell responses to UB-612 measured by ELISpot and flow cytometric assays on 14 days post 3rd dose of UB-612 will be summarized by descriptive statistics.

- **Geometric mean titer (GMT) of SARS-CoV-2 neutralizing antibody on 14 days post 3rd dose of UB-612**

GMT of SARS-CoV-2 neutralizing antibody on 14 days post 3rd dose of UB-612 and 2-sided 95% CIs will be provided for subjects who received third dose of UB-612. Summary of descriptive statistics by age group will be also performed. Analysis of GMT of SARS-CoV-2 neutralizing antibody on 14 days post 3rd dose of UB-612 for subjects received third dose of UB-612 will be performed with the Evaluable Booster Population only. For subjects received third dose of UB-612, GMT of SARS-CoV-2 neutralizing antibody on 14 days post 3rd dose of UB-612 will compare with GMT of SARS-CoV-2 neutralizing antibody on Visit 6 (pre-3rd dose baseline) by paired t test. This analysis will be performed with the Evaluable Booster Population only.

- **Geometric mean titer (GMT) of antigen-specific antibody (Anti-S1-RBD) on 14 days post 3rd dose of UB-612**

GMT of Anti-S1-RBD on 14 days post 3rd dose of UB-612 and 2-sided 95% CIs will be provided for subjects who received third dose of UB-612. Summary of descriptive statistics by age group will be also performed. Analysis of GMT of Anti-S1-RBD on 14 days post 3rd dose of UB-612 for subjects received third dose of UB-612 will be performed with the Evaluable Booster Population only. For subjects received third dose of UB-612, GMT of Anti-S1-RBD on 14 days post 3rd dose of UB-612 will compare with GMT of Anti-S1-RBD on Visit 6 (pre-3rd dose base line) by paired t test. This analysis will be performed with the Evaluable Booster Population only.

- **Geometric mean fold increase in SARS-CoV-2 neutralizing antibody and antigen-specific antibody (Anti-S1-RBD) on 14 days post 3rd dose against pre-3rd dose baseline**

GMFI and 2-sided 95% CIs will be provided. Summary of descriptive statistics by age group will be also performed. This analysis will be performed with the Evaluable Booster Population only.

- **Geometric mean titer (GMT) of SARS-CoV-2 neutralizing antibody and antigen-specific antibody (Anti-S1-RBD) on Day 57, Day 197 and Day 365 in adolescents**

The analysis of GMT of SARS-CoV-2 neutralizing antibody on Day 57, Day 197, 14 days post 3rd dose and Day 365 in adolescents will follow the analysis described above in GMT.

- **Seroconversion rate (SCR) of SARS-CoV-2 neutralizing antibody on Day 57 and antigen-specific antibody (Anti-S1-RBD) in adolescents**

The analysis of SCR of SARS-CoV-2 neutralizing antibody on Day 57 in adolescents will follow the analysis described above in SCR.

- **Geometric mean fold increase in SARS-CoV-2 neutralizing antibody and antigen-specific antibody (Anti-S1-RBD) on Day 57, Day 197, and Day 365 in adolescents**

The analysis of GMFI in SARS-CoV-2 neutralizing antibody and antigen-specific antibody (Anti-S1-RBD) on Day 57, Day 197, and Day 365 in adolescents will follow the analysis of secondary immunology endpoint in GMFI.

- Local reactions for up to 7 days following each dose in adolescents

The analysis of local reactions for up to 7 days following each dose in adolescents will follow the analysis of local reactions in primary safety endpoints.

- Systemic events for up to 7 days following each dose in adolescents

The analysis of systemic events for up to 7 days following each dose in adolescents will follow the analysis of systemic events in primary safety endpoints.

- Unsolicited AEs from Day 1 to Day 57 in adolescents

The analysis of unsolicited AEs from Day 1 to Day 57 in adolescents will follow the analysis of unsolicited AEs in primary safety endpoints.

- **MAAEs and SAEs from Day 1 to Day 365 in adolescents**

The analysis of MAAEs and SAEs from Day 1 to Day 365 in adolescents will follow the analysis of MAAEs and SAEs in primary safety endpoints.

- **AESIs and ADEs from Day 1 to Day 365 in adolescents**

The analysis of AESIs and ADEs from Day 1 to Day 365 in adolescents will follow the analysis of AESIs and ADEs in primary safety endpoints.

- Changes of safety laboratory measures in adolescents

The analysis of changes of safety laboratory measures in adolescents will follow the analysis of changes of safety laboratory measures in secondary safety endpoint.

- COVID-19 incidence per 1000 person-years of follow-up based on PCR test

COVID-19 incidence per 1000 person-years of follow-up based on PCR test will be descriptively summarized by counts, percentages, and associated Clopper-Pearson 95% CIs for each study group.

- To describe the anti-S1-RBD IgG levels and SARS-CoV-2 neutralizing titers to UB-612 in confirmed and/or severe COVID-19 cases

The anti-S1-RBD IgG levels and SARS-CoV-2 neutralizing titers to UB-612 in confirmed COVID-19 cases will be presented by descriptive summary statistics and associated 95% CIs for each study group.

- **To detect antibody against SARS-CoV-2 antigens derived from S2, N, and M protein**

The results of UBI SARS-CoV-2 ELISA will be presented by descriptive summary statistics

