10.6 Immunogenicity Evaluation

10.6.1 Analysis of Primary Immunogenicity Endpoint(s)

- Geometric mean titer (GMT) of SARS-CoV-2 neutralizing antibody on Day 57

For SARS-CoV-2 neutralizing antibody, GMT and 2-sided 95% CIs will be provided for each study group. Additionally, the difference between UB-612 vaccine and placebo groups will be analysed by ANCOVA model under log-transform data with baseline level as covariate and effect of study treatment, if appropriate. Summary of descriptive statistics by age group will be also performed.

- Seroconversion rate (SCR) of SARS-CoV-2 neutralizing antibody on Day 57

The SCR will be presented as count and percentage in frequency table, and the 95% exact (Clopper-Pearson) confidence interval will be provided as well by study group. Fisher's exact test will be used for the comparison of UB-612 vaccine group and placebo group. Summary of descriptive statistics by age group will be also performed.

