10.8 Subgroup Analysis

Additional study populations and subgroups will be assessed, with further information available in the SAP.

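### V-205 collects adolescent titres to compare with adults, but the only adolescent Day 57 test in section 10.7 is vaccine versus placebo, and no adolescent/adult contrast is estimated

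*Supplement*

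**What the plan says.** The V-205 synopsis and section 7.1 both say that the 154 evaluable adolescents are there so that their immunogenicity can be set against that of adults. Section 7.3 repeats it: "At least 154 evaluable adolescents (allocation rate 6:1) will have immune data to compare with adults". The same section ties the adolescent group to extending the vaccine's indication and announces an interim report on adolescents for that purpose. In section 10.9 this is the fourth interim analysis, a supplementary EUA dossier.

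For the analysis, section 10.7 states that the neutralizing GMT "in adolescents will follow the analysis described above in GMT", and it refers the adolescent SCR and GMFI back in the same way. The Day 57 GMT method is in 10.6.1: "the difference between UB-612 vaccine and placebo groups will be analysed by ANCOVA model under log-transform data with baseline level as covariate". For SCR, "Fisher's exact test will be used for the comparison of UB-612 vaccine group and placebo group". The GMFI method in 10.6.2 is a t test, again vaccine against placebo. By age, 10.6.1 offers only this: "Summary of descriptive statistics by age group will be also performed". Section 10.8 adds: "Additional study populations and subgroups will be assessed, with further information available in the SAP".

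The back-reference is loosely worded, because the nearest GMT text above it is the paired comparison after the third dose. For Day 57 it can only mean the vaccine-versus-placebo ANCOVA.

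**The concern.** The stated question is whether adolescents respond like adults. The named test asks whether adolescents given vaccine differ from adolescents given saline. Its null hypothesis is false for any vaccine that raises titres at all, so rejecting it does not separate an adult-like response from a much weaker one.

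What is at stake is the adolescent report meant for a wider indication. As written, it would carry a very small p-value that a reader could take as support for bridging from adults, while the quantity that bears on bridging has no planned estimate or interval. The endpoints that 10.9 lists for the first four interims include no between-age contrast.

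**Working it through.** **Inputs**
- Adolescents: 154 evaluable at 6:1, so 154 × 6/7 = 132 vaccine and 154/7 = 22 placebo (7.3).
- Young-adult vaccinees: 696 (7.4.6), or 350 × 6/7 = 300 if the lot-consistency group is left out.
- SD of log10 titre: 0.6, the planning value in 10.2.2. For sensitivity, 0.35, back-calculated from the V-122 100 µg Day 56 CI (70.764 to 149.836, n = 20; V-123 protocol, Table 5-1): (log10 149.836 − log10 70.764)/2 × √20 / t(0.975, 19 df) = 0.348.
- Adult GMT: 102.97, V-122 100 µg at Day 56 (same table).
- Placebo GMT: 2.50, assumed equal to the V-122 Day 0 value in that table.
- A common SD in both arms is assumed.

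**The plan's own figure.** The only V-205 sample size derived from titres is 115 per lot. n = 2 × SD² × (z0.975 + z0.967)² / (log10 2)² = 2 × 0.36 × (1.960 + 1.838)² / 0.0906 = 114.6, so 115. It reproduces. No calculation is given for the 154 adolescents.

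**The test that is named.** SE = 0.6 × √(1/132 + 1/22) = 0.138. Noncentrality = log10(adolescent GMT / 2.5) / SE, two-sided 5%, 152 df.

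| Adolescent GMT as share of adult | GMT | log10 difference | Noncentrality | Power |
|---|---|---|---|---|
| 1 | 103.0 | 1.615 | 11.69 | >0.999999 |
| 1/2 | 51.5 | 1.314 | 9.51 | >0.999999 |
| 1/3 | 34.3 | 1.138 | 8.23 | >0.999999 |
| 1/10 | 10.3 | 0.615 | 4.45 | 0.993 |

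Power of 80% is reached at a difference of (1.960 + 0.842) × 0.138 = 0.387. That is a GMT of 6.1, about 6% of the adult value. At SD 0.35 power is higher throughout.

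**SCR.** A 4-fold rise from 2.5 is a titre of 10. At one third of the adult GMT, the share reaching it is Φ((log10 34.3 − 1)/0.6) = Φ(0.89) = 81%, or 94% at SD 0.35. Fisher's test of 132 against 0/22 then has power above 0.999999.

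**The contrast that is not planned.** SE of the log10 ratio = 0.6 × √(1/132 + 1/696) = 0.057, or 0.063 with 300 adults. The 95% CI half-width is 10^(1.96 × SE) = 1.29-fold (1.33-fold with 300). At SD 0.35 it is 1.16- to 1.18-fold. If the true ratio is 1/3, the expected CI with 300 adults is about 0.25 to 0.44, so the deficit would be plain.

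**What a margin would cost, if one were wanted.** With equal titres and SD 0.6, the chance that the lower limit exceeds 0.5 is 99.8% (300 adults) to above 99.9% (696). For 0.67 it is 80% to 87%. The value 0.5 is borrowed from the lot criterion and 0.67 is an assumption; the documents give no margin for age.

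**The case against.** **The SAP may cover it.** Section 10.1 leaves full details to the SAP and 10.8 defers further subgroups to it. No SAP is shown, so nothing can be said about what it contains, and the point is confined to the protocol text. The deferral does not settle the matter, because 10.7 itself fixes the adolescent analysis and the test it fixes does not address the comparison announced in 7.3. The protocol also sets its other between-group titre criterion, lot consistency, in full.

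**A weak response would not be hidden.** A reader might infer that the trial could not detect a poor adolescent response. The documents do not support that. Following the adult method yields an adolescent GMT and SCR with 95% CIs, beside the adult figures. At SD 0.6, an adult GMT of 102.97 in 696 vaccinees has a CI of about 93 to 114. Adolescents at one third would show about 27 to 43. The intervals do not overlap. What is absent is an estimate of the contrast itself.

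**The endpoint is exploratory.** This is true, and a planned comparison need not be a non-inferiority test. A compulsory pass/fail margin does not follow from the documents. The result is nevertheless intended for an EUA supplement, which justifies estimating what is to be compared.

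**The elderly.** A reader might extend the point to them, since 7.3 says "at least 154 evaluable subjects will have immunogenicity data to compare with young adults". But the synopsis and 7.1 enrol the elderly immunogenicity subjects for description only, and 10.6.1 delivers descriptive summaries by age. The objection stands and the elderly are left out.

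**Later time points.** Near-certainty applies to Day 57 at V-122-like titres. If the adult GMT waned to 20, power at one third of it would be 86.9%.

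**Conclusion.** The point holds for adolescents at Day 57. The protocol announces a comparison with adults, names a test of vaccine against placebo, and plans no estimate of the adolescent/adult contrast. With 132 against 22 subjects, that test has power above 0.999999 at one third of the adult titre and 99.3% at one tenth, so its p-value is uninformative about comparability.

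This rests on the plan's SD of 0.6, an adult GMT near the V-122 value of 102.97, and placebo at the assumed 2.5. A smaller SD only strengthens it. It does not mean that the planned tables would conceal a large deficit, that the primary placebo comparison in 10.6.1 is wrong, or that a formal margin is required. It is a gap worth closing before the adolescent report is written, and the data needed are already planned.

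**What to change.** In section 10.7, or in the SAP with a reference from 10.7, add for UB-612 recipients at Day 57:
- the adolescent/young-adult GMT ratio of neutralizing antibody on log10 titres with a two-sided 95% CI, by the method 10.6.2 already uses for lots;
- the adolescent minus young-adult SCR difference with a 95% CI;
- a statement of which young adults form the reference (all 696 or the 300 outside the lot group).

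Make these the results used for the comparison with adults in the fourth interim report, and state that the adolescent placebo test is not evidence of comparability. If a comparability conclusion is to be drawn, fix and justify its margin before adolescent titres are seen. Note in the report that the age contrast is not randomised and that adolescents are enrolled after the core group.

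Leave the primary placebo comparison in 10.6.1 as it is; no change is needed for the elderly. The cost is a short text change and one extra table, with the same subjects and samples. If a margin is adopted, the claim can fail.
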